1 INTRODUCTION

1.1 Non-Hodgkin lymphoma

CD20 is a B-cell specific differentiation antigen with four transmembrane domains ([Kuijpers 2010](#)). The CD20 protein plays a critical role in normal B-cell development and is expressed on 90% of B-cell NHL ([Tedder 1988](#)).

According to National Cancer Institute (NCI), the number of new NHL cases in the United States from 2010-2014 was 19.5 per 100,000 residents per year, and the number of deaths from NHL was 5.9 per 100,000 residents per year ([SEER](#)). The NCI estimates that in 2017 there would be 72,240 new NHL cases (4.3% of all cancer diagnoses) and 20,140 deaths (3.4% of all deaths) due to cancer.

Diffuse large B-cell lymphoma (DLBCL) is the most common histologic subtype of NHL accounting for approximately 25 percent of NHL cases. In the United States, the incidence of DLBCL is approximately 7 cases per 100,000 persons per year ([SEER](#)) and varies by ethnicity, with Caucasians having higher rates than African Americans, Asians, or Native Americans.

Diffuse large B-cell lymphoma is a heterogeneous group of tumors consisting of large, transformed B cells with prominent nucleoli and basophilic cytoplasm, a diffuse growth pattern and a high (>40%) proliferation fraction. The immunophenotype of DLBCL can be confirmed by immunohistochemistry (IHC) or flow cytometry, with tumor cells generally expressing pan B cell antigens (CD19, CD20, CD22, CD79a), as well as CD45.

The prognosis for a newly diagnosed DLBCL patient depends on many host or tumor characteristics including tumor histology, tumor bulk burden and stage of tumor, participant's age and performance status. Current first line treatment for DLBCL is chemotherapy (CHOP, EPOCH, ACVBP) in combination with RTX. While 50-70% of patients are cured by current standard of care (SOC) chemotherapy (mainly R-CHOP), 30-40% of patients do not respond to R-CHOP or relapse following CR. Second line therapy with curative potential in patients with refractory or relapsed DLBCL (r/r DLBCL) is high dose chemotherapy (ICE, DHAP, GDP) + RTX followed by autologous SCT.

Before the advent of CAR-T therapy, salvage chemotherapy followed by autologous SCT was the only potentially curative therapy for patients with r/r DLBCL ([Philip 1995](#)). However, many patients do not benefit from salvage therapy because they do not respond to chemotherapy, are unfit to undergo transplants or lack caregiver support ([Crump 2014](#); [Kondo 2016](#)); a retrospective analysis (SCHOLR-1) found that only 26% of refractory patients responded to salvage therapy, and median OS was only 6.3 months ([Crump 2017](#)).

Approved third line treatment options for DLBCL include CAR-T (Yescarta® axicabtagene ciloleucel/”axi-cel”; Tisagenlecleucel/CTL019 [Kymriah®]) and antibody drug conjugates such as polatuzumab (Polivy) in combination with RTX and bendamustine. Tafasitamab (MOR208) (formerly Xmab®5574) is an anti-CD19 mAb currently investigated in patients

with r/r DLBCL who are ineligible for autologous SCT. CAR-T trials show approximately 50% ORR and approximately 30-40% durable response rate (Neelapu 2017; Locke 2019). However, CAR-T remains difficult to access for many patients, and expensive.

1.1.1 Anti-CD20 Mab therapy for NHL

Anti-CD20 mAb therapy has become a ubiquitous component of treatment regimens for B-cell malignancies. Clinically active anti-CD20 mAbs used for the treatment of NHL can be separated into two types based on cellular effects observed on binding to CD20-expressing B-cells. Type I antibodies (RTX and ofatumumab) induce redistribution of CD20 into large lipid rafts in the plasma membrane and have strong complement-dependent cytotoxicity (CDC) and antibody-dependent cell-mediated cytotoxicity (ADCC) but have minimal direct antitumor effects. Type II antibodies (tositumomab and obinutuzumab) do not induce redistribution of CD20, have minimal CDC, strong ADCC and increased direct antitumor effects. Although fully humanized mAbs should be less immunogenic than the chimeric RTX, none of the more recently approved anti-CD20 antibodies appear to be clinically more effective against NHL in direct comparisons, perhaps because of patients' baseline immune status (Maloney 2012).

Of those participants with indolent NHL who relapse >6 months after initial response to RTX, only 40% will respond again when retreated with RTX (Davis 2000). The multicenter Phase 2 CORAL (Collaborative Trial in Relapsed Aggressive Lymphoma) study showed that participants who had previously responded to a RTX containing treatment regimen had a worse outcome following RTX containing salvage immunochemotherapy.

(Gisselbrecht 2010). Most patients across all types of NHL eventually become refractory to all anti-CD20 mAb treatments. There are several mechanisms by which this can happen, including increased mAb catabolism, initial development or post-treatment selection of malignant cells with low-levels of surface CD20 expression, resistance to mAb effector mechanisms and/or impaired immune cell function (Smith 2003). CD20 can also be removed from the B-cell surface following the molecular reorganization known as trogocytosis, which occurs during the conjugation between the Fc γ receptor on B-cells and the antigen-presenting immune cells (Beum 2011).

Further, due to their relatively large size, typically, less than 0.01% of the injected dose of an anti-CD20 mAb localizes to NHL tumors in human participants (Milenic 1991).

1.2 MT-3724

MT-3724 is a recombinant homodimeric fusion protein (theoretical molecular weight of ~110 kiloDalton), where each monomer consists of a single chain variable fragment (scFv) with affinity for human CD20 cell surface protein fused to the enzymatically active Shiga-like toxin-I A1 subunit. MT-3724 specifically binds and kills CD20-expressing malignant B-cells (Rajagopalan 2013) via a novel mechanism of action of enzymatic and permanent ribosome inactivation.

As a direct-kill immunotoxin directed against CD20, MT-3724 could achieve malignant cell lysis in refractory or relapsed NHL regardless of the biologic variations of malignant B-cells or patient's immune status. The smaller size of MT-3724 may offer an advantage over anti-CD20 mAbs enabling better tumor penetration. The scFv in MT-3724 binds to a CD20 epitope within rituximab's binding domain. While able to bind to CD20, the scFv in MT-3724 lacks an intact Fc region and does not rely on host antibody-directed cytotoxicity or CDC to induce cell death. The scFv in MT-3724 should not be adversely impacted by reduction of CD20 B-cell expression via internalization or trogocytosis. Thus, MT-3724 could avoid, mitigate or delay the emergence of resistance to anti-CD20 mAb therapy and offer potential benefit in patients with unmet medical need.

1.2.1 Clinical experience with MT-3724

The clinical development program for MT-3724 is being evaluated in 3 ongoing studies: 1 monotherapy study (MT-3724_NHL_001 [NHL_001]) and 2 combination therapy studies (MT-3724_NHL_002 [NHL_002] and MT-3724_NHL_003 [NHL_003]) with gemcitabine and oxaliplatin and LEN, respectively. Further studies of MT-3724 in other subtypes of NHL are planned.

Data from the MT-3724 monotherapy study, NHL_001, showed clinical anti-tumor activity in heavily pre-treated participants with relapsed or refractory DLBCL who had low serum level of RTX before the start of treatment.

Across all 3 studies as of 18 March 2020, CLS has been reported in 5 subjects: 2 subjects from NHL_001, 2 subjects from NHL_002, and 1 subject from NHL_003. All CLS events resolved, and the maximum severity for all events was Grade 2.

Neutropenia, acute kidney injury, capillary leak syndrome (including peripheral edema, hypotension, weight gain and hypoalbuminemia), systemic inflammatory response/cytokine release syndrome, pneumonia, and viral infection were reported as AEs related to MT-3724 and identified in the Investigator's Brochure as potential risks for participants receiving MT-3724 therapy.

Please refer to the latest version of the [IB](#) for comprehensive information available for MT-3724 to date.

1.3 Lenalidomide (Revlimid®, LEN)

Lenalidomide is an analogue of thalidomide with immunomodulatory, antiangiogenic and antineoplastic activity in cancer. It was structurally designed to enhance the immunomodulatory and antitumor activity of its predecessor thalidomide and is much less neurotoxic and in general well tolerated ([Anderson 2005](#)). It is approved by the FDA and EMA for the treatment of multiple myeloma (MM), mantle cell lymphoma, transfusion-dependent anemia due to myelodysplastic syndromes associated with deletion 5q abnormality, follicular lymphoma ([FL] in combination with RTX) and marginal zone lymphoma (in combination with RTX)

The most common adverse reactions are neutropenia, thrombocytopenia, anemia, pneumonia, rash and venous thromboembolic events (predominantly deep vein thrombosis and pulmonary embolism). Allergic reactions including hypersensitivity, angioedema, Stevens-Johnson Syndrome, and toxic epidermal necrolysis were reported and fatal instances of tumor lysis syndrome have been reported during LEN treatment. Please see the reference prescribing information on LEN for additional details ([Revlimid®](#)).

1.3.1 Rituximab-lenalidomide (R²) in NHL

Following demonstration of activity in MM and chronic lymphocytic leukemia (CLL), LEN has been shown to have considerable single agent clinical activity in NHL: overall response rates in subjects with aggressive NHL are 28-35% (7-12% complete response [CR]) ([Witzig 2009](#)). Lenalidomide plus RTX (R²) has been evaluated in multiple phase II trials with variable dosing schedules and in multiple NHL subtypes ([Witzig 2015](#)).

In relapsed/refractory DLBCL or Grade 3 FL (n = 45), R² showed a 33% ORR (22% CR), a median DOR of 10.2 months, median PFS of 3.7 months, and median OS of 10.7 months ([Wang 2013](#)). In an Italian single-center phase II trial, 23 older participants (≥ 65 years) with relapsed/refractory DLBCL received LEN 20mg/day, D1-21/28 with RTX 375mg/m² on Days 1 and 21 for four cycles ([Zinzani 2011](#)). Participants with SD or better responses received LEN maintenance on the same dosing schedule for an additional eight cycles. At the end of induction, R² produced a 35% ORR and 30% CR. Of 10 participants eligible for maintenance, 8 achieved CR and a median DOR of 32 months ([Zinzani 2013](#)).

R² was generally well tolerated, with hematologic Adverse Event (AE) rates consistent with those for single-agent therapy. The rates of Grade 3/4 hematologic toxicity with R² varied across phase II studies, likely reflecting the different patient populations, NHL subtypes, and lines of therapy: neutropenia ranged from 30% to 66% and thrombocytopenia from 6% to 23% ([Wang 2012](#); [Ruan 2014](#); [Zinani 2011](#); [Fowler 2014](#)). Non-hematologic toxicity, mainly Grade 1/2, also varied across studies, mostly consisting of fatigue, myalgia, rash, and infusion related reactions.

1.4 Rationale for the study design

The overall study design includes the dose escalation in the first part and the MTD expansion cohort in the second part. This design is typically used to assess the safety and efficacy of a novel anticancer agent when it is evaluated for the first time in combination with the SOC therapy.

In Part 1, the dose decisions in sequential cohorts is based on the 3+3 design guided by the incidence of DLTs. This is the most commonly used method to identify the MTD of a novel anticancer agent in clinical trials. In Part 2, the MTD expansion cohort is also the most commonly used method to confirm the MTD and gain more data about the safety and efficacy of a novel anticancer agent in a larger number of subjects.

All efficacy and safety assessments, as well as the methods used to measure them, are standard practice in clinical studies and/or clinical practice. They are widely recognized as reliable, accurate, and relevant.

Long-term follow up will be conducted to determine the impact of MT-3724 on tumor response which is part of the secondary objectives of this study.

1.5 Benefit/risk ratio

Most patients with CD20-positive B-cell NHL will eventually become resistant to available anti-CD20 therapy. The clinical unmet need is underscored in disease areas like DLBCL where the contribution or clinical benefit of anti-CD20 antibody therapies may be diminished beyond the front-line treatment setting. As a direct-kill agent targeted to CD20, where its mechanism of action is distinct from ADCC or CDC, MT-3724 could achieve malignant cell lysis in refractory or relapsed NHL regardless of the biologic variations of malignant B-cells or patient's immune status. The current study aims to address this unmet medical need by replacing RTX in the R² regimen with MT-3724.

In vitro MT-3724 was tested in combination with LEN to assess additive, synergistic or antagonistic cytotoxic effects on a CD20-positive cell line. A synergistic effect was observed in the combination of LEN and MT-3724 tested on CD20-positive cell line (IB). This in vitro data justifies further exploring the benefit-risk of combining MT-3724 with LEN for the treatment of NHL.

In the Phase 1 first-in-human study in NHL subjects, MT-3724 monotherapy was well tolerated up to the highest dose planned for the current study (50µg/kg/dose), and the safety profile of MT-3724 has been similar to that of RTX. MT-3724 achieved objective tumor response at the lowest dose potentially used in the current study (5µg/kg/dose).

The current study will enroll subjects with advanced progressive B-cell NHL who are not eligible for any further approved NHL therapy and/or SCT and/or refuse alternative approved therapies and/or are unlikely to achieve clinical benefit from any therapy of higher priority according to the investigator's assessment. MT-3724 has a potential to impart clinical benefit when combined with the standard doses of LEN in this population. Thus, the benefit-risk ratio in the current study is acceptable.

2 OBJECTIVES AND ENDPOINTS

2.1 Primary objectives and endpoints

OBJECTIVES	ENDPOINTS
Determine the safety and tolerability (including the MTD) of MT-3724 in combination with lenalidomide in subjects with relapsed or refractory B-Cell NHL	Incidence of AEs, including DLTs, inclusive of physical exam findings, laboratory abnormalities, and/or subject-reported symptoms

2.2 Secondary objectives and endpoints

OBJECTIVES	ENDPOINTS
Characterize the PK of MT-3724 in combination with LEN in subjects with relapsed or refractory B-Cell NHL	PK parameters will be derived from MT-3724 serum concentration time data from all eligible subjects; parameters will be stratified by dose group.
Assess the PD of MT-3724 in combination with LEN in subjects with relapsed or refractory B-Cell NHL	B-cell count and immunophenotype data by flow cytometry
Assess the immunogenicity of MT-3724 in combination with LEN in subjects with relapsed or refractory B-Cell NHL	ADA NAb

Assess the tumor response to MT-3724 in combination with LEN in subjects with relapsed or refractory B-Cell NHL	Objective response based on local assessment Duration of response PFS OS
Exploratory	

3 INVESTIGATIONAL PLAN

3.1 Description of overall study design and plan

This is a multi-center, open-label, multiple-dose Phase 2a, dose-escalation study of MT-3724 in combination with LEN in subjects with relapsed or refractory B-Cell NHL. Eligible subjects will be identified and treated through competitive enrollment at multiple global study centers.

There are two sequential parts to this study. Part 1 is an evaluation of doses of MT-3724 in combination with LEN in subjects with relapsed or refractory B-cell NHL, to determine the MTD; and Part 2 is an expansion of the MTD cohort to evaluate safety, tolerability, and potential efficacy in up to 40 additional subjects with DLBCL treated with MT-3724 at the MTD in combination with LEN. For LTFU, subjects from both parts of the study will be followed for 18 months from the last dose of MT-3724, see study design in [Figure 1](#).

In both parts of the study, the subject's participation in the study will consist of 4 periods: Screening, Treatment, STFU, and LTFU.

3.2 Screening

Screening procedures will be performed within 35 days before the start of treatment on C1D1, with the exception of laboratory safety and radiographic assessments which are to be done within 28 days of C1D1. A signed written informed consent form (ICF) will be obtained before any screening procedure may begin. Screening assessments will be the same for Part 1 and Part 2.

After the investigator determines that all eligibility criteria have been fulfilled ([Section 4.1](#) and [Section 4.2](#)) the medical monitor will review the screening results and acknowledge that the subject may enter the treatment phase of the study.

3.3 Treatment

Each subject may be treated only in one part of the study. The treatment procedures will be identical in Part 1 and Part 2.

3.3.1 MT-3724

MT-3724 will be administered as an IV infusion over 1 hour (54 to 75 minutes).

Treatment with MT-3724 will be administered for cycles of 28 days each until death, disease progression, unacceptable toxicity, withdrawal of consent or another reason for withdrawal, or until study discontinuation.

3.3.2 Lenalidomide

In both parts of the current study, subjects will self-administer LEN qd PO with or without food, around the same time each day, on the first 21 consecutive days (D1-D21) of each 28-day cycle. LEN cannot be administered between D22-D28 in any cycle.

3.4 End of Treatment Visit and Short-Term Follow-Up phone call

The EoT Visit will be performed at the end of the treatment period for each subject in Part 1 and Part 2. The EoT Visit should occur at the time of discontinuation, as soon as possible after the last dose of MT-3724 or LEN (within 14 days of last dose) for all subjects, except those who withdrew consent and objected to further data collection, or were lost to follow up.

The EoT Visit should be performed during the clinic visit. The EoT Visit may be performed by telephone call, but only if a subject cannot attend a clinic visit or has started a new anticancer treatment. In such instances, missed assessments (e.g., laboratory assessments, PE), are not considered deviations.

The STFU phone call will take place at least 30 days (+7 days) after the last dose of MT-3724 or LEN (except for subjects who withdrew consent and objected to further data collection, or were lost to follow up).

3.5 Long-Term Follow Up Visit

The LTFU Visits should occur every 3 months (\pm 14 days) for up to 18 months from the last dose of MT-3724. Subjects who discontinue treatment for disease progression will be followed only for OS. Subjects who discontinue for reasons other than disease progression (e.g., toxicity) will be followed for PFS and OS. Subjects with CR, PR, or SD should also be followed for radiology assessment until progressive disease, death, or start of new anticancer treatment. The LTFU Visits will be performed via a telephone call to collect the information about death (if any), the NHL status (relapsed or not) and the start of any new therapy for NHL or any other investigational drug since the last study visit/phone call and radiology data should be obtained from medical records.

Cohort management and dose escalation decisions (including the MTD) will be based on the incidence of TEAEs that fulfill the criteria for a DLT, as follows:

- The first dose escalation decision in the current MT-3724 dose cohort will be made after at least 3 subjects complete cycle 1 or experience a DLT. Up to 4 subjects may be initially treated in each MT-3724 dose cohort; this aims to ensure that at least 3 evaluable subjects are available for the first dose escalation decision.
- If none of the first 3 or 4 subjects in the current MT-3724 dose cohort experience a DLT, then dose escalation may proceed to the next planned MT-3724 dose level.
- If 1 of the initial 3 or 4 subjects in the current MT-3724 dose cohort experiences a DLT, then this cohort will be expanded to 6 subjects. Subjects for the expanded current cohort may be enrolled simultaneously through competitive enrollment.

- d. If no more than 1 of 6 subjects in the expanded current MT-3724 dose cohort experiences a DLT, then dose escalation may proceed to the next planned MT-3724 dose level.
- e. If a DLT occurs in ≥ 2 of initial 3 or 4 subjects in the current MT-3724 dose cohort, or in ≥ 2 of 6 subjects in the expanded current cohort, one of the following 2 steps may be undertaken at the sponsor's discretion after consultation with the investigator(s):
 - If not previously done, up to 6 subjects may be treated at the planned MT-3724 dose level immediately below the non-tolerable dose.
 - Alternatively, up to 4 subjects may be initially treated at the 'interim' MT-3724 dose level and schedule between the non-tolerable dose level and the planned MT-3724 dose level immediately below the non-tolerable dose. The MT-3724 doses proposed for the 'interim' cohorts are listed in [Table 5](#); however the actual MT-3724 doses and schedule for 'interim' cohorts will be recommended by the sponsor after consultation with all investigators.
- f. If at least 4 subjects in the cohort have no DLTs, dose re-escalation can be attempted in up to 6 subjects at the original target dose of the previous cohort under the new schedule after consultation with the investigators and medical monitor.
- g. The same principles as listed above will apply to the cohort management and dose decisions in the 'interim' MT-3724 dose cohorts.

Treatment in the expanded current MT-3724 dose cohort or the next cohort may start only after the dose decision in the current cohort has been made; however, prospective subjects may be consented and screened during the review of the safety data leading to the dose decision.

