3.6.1 Subject evaluable for dose decisions

Subjects in Part 1 will be evaluable for dose decisions if they satisfy one of the following criteria:

- Have had a DLT after at least one dose of MT-3724 in cycle 1; or
- In the absence of DLT, have received at least 4 of 6 (67%) doses of MT-3724 (if 6 doses are planned) or 3 of 4 doses (75%) of MT-3724 (if 4 doses are planned) and at least 14 of 21 (67%) doses of LEN.

Subjects who are not evaluable for dose decisions will be replaced.

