4.3.2 Subject replacement

In both parts of the study, the sponsor will determine if a subject should be replaced. All subject data collected will be analyzed in the Safety Analysis set. The additional subject(s) included to replace non-evaluable subjects will be given new unique subject IDs.

Part 1 (MT-3724 Dose Escalation)

Subjects who discontinue in cycle 1 and are not evaluable for dose decisions ([Section 3.6.1](#)) must be replaced in the current dose cohort to ensure that a sufficient number of subjects are available for dose decisions. Non-evaluable subjects may remain on treatment if supported by the investigator's assessment of the benefit-risk ratio after consultation with medical monitor.

Subjects who discontinue for any reason after cycle 1 will not be replaced.

Part 2 (MTD Expansion Cohort)

Subjects in Part 2 of the study who have insufficient safety, PD, PK or immunogenicity data in cycle 1 may be replaced at the sponsor's discretion, unless they experienced a TEAE leading to treatment modification.

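### Section 3.6.1 counts a DLT-free subject on doses received, without DLT follow-up to the end of cycle 1, so a subject lost mid-cycle can support escalation

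*Protocol*

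**What the plan says.** The protocol uses two tests for who counts in a Part 1 dose decision.

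- **Observation test.** Rule (a) in section 3.6 allows the first escalation decision "after at least 3 subjects complete cycle 1 or experience a DLT". Section 3.6.3 applies the same condition to at least six subjects before an MTD is declared.
- **Dose-count test.** Section 3.6.1 defines evaluability: "In the absence of DLT, have received at least 4 of 6 (67%) doses of MT-3724" on the six-dose schedule, or "3 of 4 doses (75%) of MT-3724 (if 4 doses are planned"), and in either case "at least 14 of 21 (67%) doses of LEN". It states no observation time.

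Rule (a) itself mixes the two. After setting the observation gate, it explains that up to four subjects may be treated because "this aims to ensure that at least 3 evaluable subjects are available for the first dose escalation decision". Rules (b), (c), (d) and (f) refer only to subjects; rule (d), for example, reads "If no more than 1 of 6 subjects in the expanded current MT-3724 dose cohort experiences a DLT".

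On replacement in Part 1, section 4.3.2 makes it mandatory for this group: "Subjects who discontinue in cycle 1 and are not evaluable for dose decisions". Section 3.6.1 ends by saying that all non-evaluable subjects are replaced. Section 5.10 identifies the DLT assessment period as cycle 1, and cycles last 28 days.

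SAP 5.4 carries a different version of the dose-count test, also with no observation condition. It prints 4 of 6 as 83% and asks for both doses of lenalidomide, a drug taken daily for 21 days.

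**The concern.** In a 3+3 design, every subject counted as DLT-free should have been at risk and under observation for the whole assessment period. Someone observed for only half of it has had less opportunity to show a DLT, but enters the count as a full negative. Cohorts hold three to six subjects and DLT incidence drives each escalation decision, so one such subject can change the outcome. The error runs one way, toward escalation.

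Replacement does not close the gap. Once the dose counts are met, the subject is evaluable, so 4.3.2 does not oblige the sponsor to replace them.

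**Working it through.** **1. The plan's own figures.** 4/6 = 66.7%, 3/4 = 75.0% and 14/21 = 66.7%, so the percentages in 3.6.1 reproduce. The 83% in SAP 5.4 does not: it corresponds to 5/6 = 83.3%.

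**2. Earliest day on which a DLT-free subject is evaluable** (dosing days from Protocol 5.1.3 and 5.2.2).

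- Cohorts 1-3, Days 1, 3, 5, 8, 10, 12: fourth MT-3724 dose on Day 8.
- Later cohorts, Days 1, 5, 8, 12: third MT-3724 dose on Day 8.
- Lenalidomide daily from Day 1: fourteenth dose on Day 14.
- Evaluable from max(8, 14) = Day 14, with 28 - 14 = 14 days of the cycle still to run. Dosing days may move, so Day 14 is the earliest nominal day.

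**3. Which test applies where.**

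| Place | Condition on a DLT-free subject |
|---|---|
| Rule (a), gate | finishes cycle 1 |
| Rule (a), stated aim | evaluable |
| Rules (b)-(d), (f) | none stated |
| 3.6.1 | dose counts |
| 3.6.3 | finishes cycle 1 |
| 4.3.2, mandatory replacement | follows 3.6.1 |
| SAP 5.4 | dose counts, worded differently |

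A subject lost after Day 14 cannot be one of the three in rule (a) or the six in 3.6.3. They can be a fourth initial subject, one of those added before rule (d) is applied, or one of the four in rule (f).

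**4. Size, as an illustration.** The documents give neither a true DLT risk nor its timing, so both are assumptions. Let p = 0.33 be the cycle-1 DLT risk and q the part of it that falls before a lost subject leaves.

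P(escalate) = P(0 DLT in first 3) + P(1 DLT in first 3) × P(0 DLT in 3 added)

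- P(0 in 3) = 0.67³ = 0.3008; P(1 in 3) = 3 × 0.33 × 0.67² = 0.4444.
- All fully observed: 0.3008 + 0.4444 × 0.3008 = **0.434**.
- Constant hazard, leaving at Day 14: q = 1 - 0.67^0.5 = 0.181.
- One lost subject among the three added: 0.3008 + 0.4444 × 0.8185 × 0.67² = **0.464**.
- All three added subjects lost: 0.3008 + 0.4444 × 0.8185³ = **0.544**.

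Varying the share of risk that falls before leaving (q = share × 0.33):

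| Share before leaving | One of three added | All three added |
|---|---|---|
| 25% | 0.484 | 0.644 |
| 50% | 0.467 | 0.559 |
| 75% | 0.451 | 0.490 |

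Varying the true risk, with one lost subject among the three added:

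| True risk | Fully observed | Share 75% to 25% |
|---|---|---|
| 20% | 0.709 | 0.721 to 0.745 |
| 33% | 0.434 | 0.451 to 0.484 |
| 40% | 0.309 | 0.325 to 0.356 |
| 50% | 0.172 | 0.184 to 0.207 |

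**5. Fourth initial subject (4 + 2), p = 0.33.** Fully observed: 0.67⁴ + (4 × 0.33 × 0.67³) × 0.67² = 0.2015 + 0.3970 × 0.4489 = 0.380. With one of the four lost, P(0) = 0.67³(1 - q) and P(1) = 0.4444(1 - q) + 0.3008q. The result is 0.470, 0.440 or 0.410 for shares of 25%, 50% or 75%.

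**The case against.** The case against is substantial, and much of it stands.

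- **MTD declaration.** A reader might infer that an MTD could be declared on partly observed subjects. Section 3.6.3 does not allow it: six subjects must finish cycle 1 or have a DLT. The exposure is in escalation.
- **Leaving is not the same as being unobserved.** Adverse events are collected until the short-term follow-up call, at least 30 days after the last dose (Protocol 3.4, 6.3.1). After a last dose on Day 14, that is Day 44 or later. Starting a new anticancer therapy does not end collection of events believed related to MT-3724, and a DLT must be at least possibly related to it. The gap is therefore mainly loss to follow-up, or withdrawal of consent with objection to further data. Section 3.6.1 does not separate these cases from simply stopping treatment.
- **Under-dosed completers.** A reader might also infer that someone who finishes cycle 1 on too few doses is counted. The last sentence of 3.6.1 says such a subject is replaced. Only 4.3.2, whose mandate covers discontinuations, needs aligning.
- **Discretion.** The sponsor may replace more subjects than 4.3.2 requires, escalation is permitted and not compelled, and a consensus review of all available data comes first. These are real safeguards, but none defines the denominator.
- **Timing of risk.** Nominal MT-3724 dosing in cycle 1 ends on Day 12, and Appendix 9 describes innate immune responses as typically early in that cycle. Front-loaded risk favours the smaller figures (0.451 at a 75% share).
- **Choice of measure.** It is tempting to use P(at most 1 DLT in 6), which goes from 0.358 to 0.461 with two lost subjects and 0.518 with three. That is not the 3+3 escalation probability: three initial subjects without a DLT already permit escalation.

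**Conclusion.** The inconsistency is real and narrow. Section 3.6.1 has no observation condition, 4.3.2 relies on 3.6.1, and rules (b)-(d) and (f) do not restore the condition found in rule (a) and 3.6.3. A subject lost to observation between Day 14 and Day 28 can therefore be counted as DLT-free in an escalation decision.

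At an assumed 33% risk, one such subject among the three added increases the escalation probability by 0.030 under constant hazard (0.464 - 0.434), and by 0.017 to 0.050 over the range of timings shown. The increase of 0.110 when all three are lost is an extreme case. The direction is upward whenever some risk remains after leaving; the size depends wholly on the assumed risk and timing. It also assumes that later events go unseen, and that cycle 1 means 28 days, since the protocol does not define completing it.

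The text also leaves a practical impasse. If three subjects are treated and one is lost on Day 15, rule (a) is not met, yet 4.3.2 does not require a replacement. The point is worth correcting because DLT counts drive Part 1 and the remedy is wording.

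**What to change.** 1. In 3.6.1, add that a DLT-free subject must also have DLT follow-up through the end of cycle 1, whether on or off treatment.
2. Use 'evaluable subjects' in rules (a)-(f) and in 3.6.3. With item 1 in place, this keeps the observation requirement that rule (a) and 3.6.3 now carry.
3. Align 4.3.2 with 3.6.1, so that every Part 1 subject not evaluable under the revised definition is replaced.
4. Reconcile SAP 5.4 with the same definition, including the 83% and the lenalidomide count. SAP section 4 gives the SAP's statistical methods precedence over the protocol, so two versions should not stand.

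The cost is wording plus an occasional extra replacement in Part 1. No dose or treatment rule changes.
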